#### 16. LIMITATIONS AND UNCERTAINTIES:

Men undergoing device VMMC are excluded, limiting generalizability to surgical VMMC. Phone ownership in RSA's urban areas is high, but there is a small possibility that the population who undergoes VMMC has lower than estimated phone access, reducing the potential efficiency of a texting approach to follow-up. While evidence from Kenya and elsewhere suggests that patients are likely to interact with health professionals via SMS, it is possible that a higher than estimated percentage of clients will not respond to SMS, increasing the need for follow- up by voice calls, thus reducing the efficiency and cost gains afforded by the intervention. Lastly, we anticipate some challenges in program implementation such as network outages (though these are increasingly fewer and shorter) and user error, but previous Medic Mobile experience and the expert local team will enable swift identification of bottlenecks and appropriate, real-time, solutions.

#### 17. INTENDED USE OF FINDINGS

This project will evaluate the effectiveness, feasibility, and acceptability of a promising intervention to improve VMMC efficiency while maintaining patient safety. If successful, both providers and patients would neither perform nor attend unnecessary visits, providing distinct advantages to both groups. These advantages could be scaled up if the approach is adopted by the NDOH, providing population-levels gains to millions of providers and patients of the VMMC program.

#### 18. STUDY TIMELINE

We expect the study to start immediately after the IRB approvals, technology adaptation, and pilot-driven modification. We aim to complete recruitment by June, 2021 in order to compete primary data analysis in July 2021. Objectives 2 and 3, as well as much of the statistical analyses will be conducted in years 1 and 2.

#### 19. BUDGET

This project will cost approximately \$500,000.

**Expanding and Scaling Two-way Texting to Reduce Unnecessary Follow-Up and
Improve Adverse Event Identification Among Voluntary Medical Male
Circumcision Clients in the Republic of South Africa**

NCT04327271

[name], Principal Investigator

Statistical Analysis Plan (PDF/A) Version Date 8/26/19

Sample size and power:

RCT to determine no inferior AE ascertainment using 2-way texting rather than routine care. Randomization will be 1:1 between routine care and the texting intervention. If routine care AE ascertainment is 0.5% as evidenced from Aurum Institute program records, and 2-way texting increases AE ascertainment to 2.0% similar to our intervention arm AE ascertainment rate for the same intervention in our prior study in Zimbabwe (1.88%), and if we take -0.25% to be our noninferiority margin, and assume 10% LTFU, enrolling 1,104 men will give 80% power to establish noninferiority. In other words, 1,104 men (at least 994 of whom provide analyzable data) will provide at least 80% power to rule out a decrease of more than 0.25% based on the lower bound of the one-sided 95% confidence interval for the difference between arms in the proportion with AEs ascertained.

Sample sizes required to establish noninferior AE ascertainment using 2-way texting.

AE ascertainment		Sample size required for 80% power*		
Routine Care	2wText	N/group	Total N	+ 10% increase for LTFU
0.5%	1.50%	782	1564	1738
0.5%	2.00%	497	994	1104

* Calculated using Statistical Solutions Nquery Advisor version 8.4.1.0, two-group test of non-inferiority in proportions.

DATA ANALYSIS:

1. For the 2wT safety outcome of interest is cumulative AE rate (moderate or severe) \leq Day 14. In RSA, and similar to other countries in the region, moderate AEs are those which include symptoms requiring modification of activity, but not resulting in loss of work or cancellation of social activities while severe AEs are those with incapacitating symptoms, requiring bed rest and loss of work ¹. Incidence of AEs before Day 14 will be extracted from routine VMMC data for both 2wT and control. Incident AEs on Day 14 will be identified, classified, and graded for severity using routine NDOH protocols ² and recorded on routine VMMC AE forms.

To test our noninferiority hypothesis, we will compare cumulative proportion (rate) of any moderate or severe AE ascertained \leq Day 14 between groups by comparing the lower limit of the one-sided 95% confidence interval of the difference in proportion between groups, to the noninferiority margin. The rates will be calculated per arm as: (# moderate + severe AEs)/(total # MC clients who attend 2, 7 or 14 Day follow-up visit). Based on our RCT in Zimbabwe, we may actually observe an increase in AEs; in that case, we will then seek to establish superiority of the two-way texting group by comparing arms with Fisher's exact test. While our study design provides limited power for this comparison (45%), there's no statistical impediment to performing both noninferiority and superiority comparisons in a noninferiority trial. To determine follow-up visit reduction, we will compare the mean number of in-person visits for intervention and control using a t-test. A multivariate linear regression model will further quantify the effect of intervention on visit reduction, adjusting for potential confounders. Secondary outcomes include: AE rates on Day 14, texting response rate, time between 2wT AE text reporting and follow-up, severity of AEs. We will perform appropriate summaries of missing data and LTFU, testing for systematic differences in response by study arm. We will examine individual mediating (e.g., referral follow-up, response rate) and moderating (urban/rural) variables ³. *We hypothesize that 1) 2wT is non-inferior to routine follow-up for patient safety and that 2) 2wT will reduce unnecessary follow-up over standard care.*

2. For 2wT acceptability, using study recruitment and enrollment logs in addition to the texting database, we will describe levels of acceptance, participation, refusal and drop-out. We will carry out key informant interviews (KIIs) with up to 10 health care workers to gauge acceptability, satisfaction, identify facilitators and barriers to program success, and ascertain suggestions for intervention improvement. KIIs will be audio recorded and transcribed. Atlas.Ti software will be used to create a spreadsheet of key themes, perceived barriers, and suggested facilitators to the program from KIIs. We will also implement questionnaires at the Day 14 visit with a subset of 100 2wT VMMC clients in the main study who were randomized to texting to gauge satisfaction, estimate direct and indirect costs (time away from work, transportation costs), and ascertain suggestions for intervention improvement. Responses from these brief, self-administered, quantitative surveys with VMMC clients will be entered in Excel and frequencies explored in STATA 12.0. For feasibility, costing data will be combined with usability and acceptability information. These comprehensive data will be discussed at a final stakeholder meeting to disseminate study results, validate interpretations and refine recommendations for future scale up and modification of 2wT in RSA and beyond. Additional meetings between local researchers and the NDOH will further determine feasibility for replication and scale-up. *We hypothesize that acceptability, usability, and feasibility will be high, aiding program scalability.*

3. For 2wT costs, we will calculate the relative costs and outcomes (effects) of intervention versus control, including costs for technology, healthcare worker time, and client considerations (travel, text costs, missed work). We will conduct both activity-based costing from the implementation perspective and from the technology perspective to extrapolate our results as costs that would be incurred by the NDOH should they elect widespread scale up of 2wT. **Approach for costing.** First we quantify the total direct and indirect costs of 2wT deployment, a method previously used for technology cost assessment in Malawi ⁴, which includes comprehensive costs from installation and training, routine maintenance, healthcare worker time associated with 2wT, and staff efficiency gains/losses in addition to the direct cost of technology. Second, we will estimate incremental costs (incremental relative to standard practice) for the intervention. This component entails a micro-costing study using activity-based approaches for costs incurred (trainings, VMMC service provision, follow-up) and costs averted (health costs for providers and patients saved by reducing visits), adapting previous VMMC costing estimates ⁵ for 2017 dollars when appropriate. Cost data will also be collected from the study budget, public health clinic budgets, published government reports, and the health economics literature. Lastly, to estimate the cost savings associated with 2wT over routine VMMC follow-up, we will conduct a time-motion study ^{6,7} to quantify time spent for VMMC follow-up, indicating potential time savings for providers and VMMC clients. One trained observer will record VMMC client/provider follow-up interactions for 5-10 days, or approximately 100 reviews, recording times and activities using a pre-established checklist and timing system. During these same 5-10 days, client time from registration through visit completion will be recorded by a second observer. Data will be exported into STATA 12.0 for analysis. The combined, overall costs for the delivery of 2wT in public health clinics will be estimated and compared to standard follow-up. *We hypothesize that 2wT will reduce the costs associated with VMMC patient follow-up over standard care.*

1. Department of Health of the Republic of South Africa. *South African National Guidelines for Medical Male Circumcision*. Department of Health of the Republic of South Africa,;2016.

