#### 4. GOAL AND OBJECTIVES

We propose to maintain patient safety while reducing the substantial VMMC follow-up workload burden by using two-way mobile phone texts to provide in-person review only for men who indicate a desire or need for follow-up. This tailored approach to post-procedure VMMC care could reduce unnecessary visits and remove barriers for VMMC clients without deterioration of quality care. I-TECH's diverse, expert team of researchers from the University of Washington, Seattle, USA; Aurum Institute's office in Johannesburg; and Medic Mobile, Nairobi, Kenya, will test this mHealth intervention. We believe that bi-directional, interactive, text-based short message service (SMS) during the most critical 14 days after circumcision will help men identify and act on any sign of an adverse event, thereby seeking in-person follow-up only when an AE is suspected and reducing unnecessary visits. Reduced in-person follow-up could also free healthcare workers to perform additional **VMMC** surgeries. Using a prospective, randomized control trial (RCT), our intervention compares two groups of clients with cell phones: 1) standard care (control group) and 2) clients who receive and respond to a daily text with in-person follow-up only if desired or if an AE is suspected (intervention). Both arms complete a study-specific, Day 14, in-person, follow-up review for verification of self-reports (intervention) and comparison (control). Our specific objectives are to:

Objective 1: Determine if 2-way texting can safely reduce VMMC follow-up visits

Approach: Un-blinded, prospective, non-inferiority, RCT in high-volume facilities providing VMMC. Two-way texting (**2wT**) will provide interactive, text-based follow-up. 2wT men healing without complication could decline in-person follow-up; those with suspected AEs will be referred to in-person care. We will compare the safety outcome of combined moderate or severe AE rate ≤ Day 14 post-VMMC and the workload outcome of average number of in-person follow-up visits between control and intervention arms.

Objective 2: Estimate the cost savings associated with 2wT over routine VMMC follow-up

Approach: We will determine the programmatic costs of 2wT from a systems perspective, including the technology , healthcare worker costs, and client perspective (travel, text costs, missed work). We will estimate the incremental

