#### 10. DATA ANALYSIS:

For Objective 1, the 2wT safety outcome of interest is cumulative AE rate (moderate or severe) ≤ Day 14. In RSA, and similar to other countries in the region. moderate AEs are those which include symptoms requiring modification of activity, but not resulting in loss of work or cancellation of social activities while severe AEs are those with incapacitating symptoms, requiring bed rest and loss of work 66. Incidence of AEs before Day 14 will be extracted from routine VMMC data for both 2wT and control. Incident AEs on Day 14 will be identified, classified, and graded for severity using routine NDOH protocols  and recorded on routine VMMC AE forms. We will compare cumulative rates of any moderate or severe AE ≤ Day 14 between groups using Fisher's exact test as the expected number of AEs is low. The rates will be calculated per arm as: (# moderate + severe AEs)/ (total # VMMC clients who attend/responded to 2, 7 or 14 Day follow-up visits or texts). Multivariate logistic regression models (any AE v none) will quantify the magnitude of difference, adjusting for any potential confounders. To determine follow-up visit reduction, we will compare the mean number of in-person visits for intervention and control using a t-test. A multivariate linear regression model will further quantify the effect of intervention on visit reduction, adjusting for potential confounders. Secondary outcomes include: AE rates on Day 14, texting response rate, time between 2wT AE text reporting and follow-up, severity of AEs. We will perform appropriate summaries of missing data and LTFU, testing for systematic differences in response by study arm. We hypothesize that 1) 2wT is non-inferior to routine follow-up for patient safety and that 2) 2wT will reduce unnecessary follow-up over standard care.

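### Protocol and SAP give different analyses for the same Day 14 safety outcome: Fisher's exact test in one, a confidence limit against a -0.25 point margin in the other, and neither document says which governs

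*SAP*

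**What the plan says.** The protocol's Objective 1 (section 4) describes a "prospective, non-inferiority, RCT in high-volume facilities providing VMMC". Section 10 compares cumulative moderate or severe AEs to Day 14 "between groups using Fisher's exact test as the expected number of AEs is low". It adds logistic models that "will quantify the magnitude of difference, adjusting for any potential confounders". The same paragraph ends with the hypothesis that "2wT is non-inferior to routine follow-up for patient safety". No margin, confidence-limit rule or significance level appears in that section.

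The SAP repeats the hypothesis but tests it "by comparing the lower limit of the one-sided 95% confidence interval of the difference in proportion between groups, to the noninferiority margin". Its sample-size section sets the margin at -0.25% and says that the planned enrolment "will provide at least 80% power to rule out a decrease of more than 0.25" percent. Fisher's test comes in only as a second step: "we may actually observe an increase in AEs; in that case, we will then seek to establish superiority of the two-way texting group".

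The denominators differ as well. Protocol section 10 counts men who came to a Day 2, 7 or 14 visit or who answered a text. The SAP counts only men who attended a visit.

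**The concern.** The two analyses answer different questions. Fisher's test asks whether the data are compatible with equal rates. The SAP rule asks whether a fall in AE ascertainment of more than 0.25 points can be ruled out. With few events, Fisher's test is non-significant for almost any plausible result, including results that fail the margin.

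Texting replaces scheduled in-person visits, and the findings are meant to inform national follow-up schedules, so the safety conclusion rests on this comparison. The same data could be reported as no significant difference under the protocol and as non-inferiority not shown under the SAP. There is no precedence statement, and protocol section 12 requires conduct in line with the protocol unless an amendment is approved. The choice could therefore be made, or appear to have been made, after the results are known.

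**Working it through.** **Inputs.** From the SAP's sample-size section: control rate 0.5%, texting rate 2.0%, margin -0.25 points (texting minus control), one-sided 95% limit, 80% power, 497 analysable men per arm, 10% loss to follow-up, 1,104 enrolled (552 per arm). Assumed: Fisher's test two-sided at 0.05, because protocol section 10 gives no level; a Wald interval, because the SAP names no method.

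**The plan's own figure.** With unpooled variance,

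n = (1.645 + 0.8416)² × [0.005 × 0.995 + 0.02 × 0.98] / (0.015 + 0.0025)² = 6.183 × 0.024575 / 0.00030625 = 496.1, so 497 per arm.

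Total 994, and 994 / 0.9 = 1,104.4, in line with 1,104. The 0.5% v 1.5% row gives 781.5, so 782, also as printed. The SAP's calculation is sound.

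**Both analyses on the same counts.** Wald lower limit = d - 1.645 × √{[pc(1 - pc) + pt(1 - pt)] / n}. About 2 and 10 events per arm correspond to 0.5% and 2.0% of 497.

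- 2 v 2: p = 2/497 = 0.00402 in each arm, d = 0. Limit = -1.645 × √(0.008016 / 497) = -0.00661.
- 10 v 10: p = 10/497 = 0.02012 in each arm, d = 0. Limit = -1.645 × √(0.03943 / 497) = -0.01465.
- 6 v 2: d = 4/497 = 0.00805. Limit = 0.00805 - 1.645 × √(0.015935 / 497) = -0.00127.

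| Texting v control, 497 per arm | Fisher p | Lower limit, Wald (points) | Lower limit, score (points) | Above -0.25? |
|---|---|---|---|---|
| 2 v 2 | 1.00 | -0.66 | -0.85 | no |
| 10 v 10 | 1.00 | -1.47 | -1.55 | no |
| 5 v 2 | 0.45 | -0.27 | -0.33 | no |
| 6 v 2 | 0.29 | -0.13 | -0.15 | yes |

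At 552 per arm the Wald limits are -0.60 for 2 v 2 and -1.32 for 10 v 10, so both still miss the margin. A non-significant Fisher result occurs both where the margin is met (6 v 2) and where it is missed (the other rows), so it does not indicate which verdict the SAP rule would give.

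**How often this happens.** Enumerating count pairs with binomial weights, 497 per arm, Wald limit:

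| True rates, control / texting | Fisher non-significant | Non-significant and margin missed |
|---|---|---|
| 0.5% / 0.5% | 99.1% | 85.0% |
| 2.0% / 2.0% | 96.9% | 89.9% |
| 0.5% / 0.25% (half of AEs missed, assumed) | 98.7% | 89.6% |
| 0.5% / 2.0% (design) | 52.8% | 16.2% |

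At a 0.5% control rate, Fisher's test hardly separates equal ascertainment (99.1% non-significant) from texting that misses half of AEs (98.7%).

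**The case against.** Three points count against the concern.

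First, section 10 never says that Fisher's test is the test of non-inferiority, nor that a non-significant result would be read as safety. A reader might infer both, because it is the only hypothesis test named for this outcome and the hypothesis closes the same paragraph. The documents do not support going further. What stands is that section 10 names no analysis that answers its own hypothesis.

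Second, a reader might infer that the protocol has no margin at all. That cannot be claimed. The sample-size heading in section 9 has no text in the supplied copy, and references 62 to 65, two of them methods papers on non-inferiority trials, are cited nowhere in what survives. Non-inferiority text, perhaps with a margin and a decision rule, probably stood there. The point is therefore limited to the surviving text of section 10. The difference in named tests remains, although missing text might have explained how they relate.

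Third, the SAP already has a workable rule with margin, direction and level, so what remains is alignment. That is right, and it keeps the repair small. It does not remove the conflict, because nothing says that the SAP prevails. The interval method and the wording for a failed margin are refinements and not part of the contradiction.

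**Conclusion.** The contradiction holds. For one outcome and one hypothesis, protocol section 10 names Fisher's test and a logistic model, while the SAP names a margin rule and reserves Fisher's test for superiority. On identical data they can support different statements: in about 85% of trials with both arms at 0.5%, Fisher's test is non-significant while the margin is missed. That figure assumes 497 per arm, a Wald limit and a two-sided 0.05 level; with a score limit it is about 88%.

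The 85% should not be read as a flaw in the SAP rule or as a sign of missed AEs. The trial was powered for an expected rise from 0.5% to 2.0%, so with truly equal arms the margin is usually missed. The 80% power claim is correct at the stated rates.

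The calculations also assume one denominator, which the documents do not share: men who only text count in the protocol's rate and not in the SAP's. Leaving out such men, if they have no recorded AE, raises the texting rate. Aligning the test alone would therefore still leave two different primary rates.

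**What to change.** Before analysis:

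1. In protocol section 10, make the SAP rule the primary safety analysis: texting minus control, one-sided 95% lower limit against -0.25 points.
2. Limit Fisher's test to the SAP's superiority step and label the logistic model supportive.
3. State that a non-significant Fisher test is not evidence of non-inferiority.
4. Use one denominator in both documents, saying explicitly whether men who only text are counted.

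Optional: name the interval method and report the two-sided 90% interval, whose lower limit is the one-sided 95% limit. A score-type interval suits small counts; Wald has zero width at 0 v 0 and would pass the margin there. At 497 per arm the two methods give different verdicts at four count pairs (0 v 0, 1 v 0, 7 v 3, 35 v 24), which is 2.6% of trials with both arms at 0.5%.

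No change is needed to the margin, the enrolment or the power statement. The cost is a short protocol edit with its approval and a matching line in the SAP, with no new data, visits or participants. The sponsor gives up any safety claim from a non-significant Fisher test.

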VMMC care procedures (2wT arm): We will conduct a prospective, un-blinded, randomized control trial (RCT) among VMMC clients in a 1:1 ratio of control to intervention. Study participants and clinic staff are not masked to treatment. For the 552 men randomized into the intervention arm, men in the 2wT will receive routine VMMC surgical care and counseling, including referral cards for emergencies. 2wT clients will receive automated daily texts from days 1-14 (Table 1 and Figure 3). It is free to receive call and texts; it costs approximately R0.20 to send a SMS in RSA . If they respond that they suspect no adverse event, no immediate follow-up action will be taken. If a 2wT VMMC client responds affirmatively to any daily text that he

[figure not shown]
suspects an AE, a VMMC nurse will exchange modifiable, scripted texts with the client to determine the symptoms, frequency, and severity. Then, if deemed necessary, the client will be asked to return to clinic the following day or earlier if an emergency is suspected. AE management will adhere to NDOH standard care. If 2wT patients do not respond to texts on Day 2 or Day 7, the same NDOH tracing process will be activated on Day 14, after which they will be considered LTFU. All study participants will be asked to come to the clinic for study-specific, Day 14 follow-up to review healing and verify adverse event reporting. Day 14 was chosen for verification because 95% of all AEs within a similar VMMC program in Zimbabwe are reported Day 14 or earlier 61, suggesting that most AEs have occurred by this time point. In a previous field study of AEs, the most common AEs of bleeding and infection were found a mean of 6.7 and 9.0 days, respectively, after VMMC , further supporting the 14 day period used in this and a previous study. The Day 14 review will be conducted by routine VMMC providers according to NDOH review guidelines. At Day 21, we will implement a brief text-based survey with 2wT clients to ascertain complete healing, providing stronger inferences at study completion.

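### The primary rate formula counts adverse events, while the planned tests and the sample size need the number of men with at least one

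*SAP*

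**What the plan says.** The only explicit formula for the primary rate is in the SAP, Data Analysis item 1: "The rates will be calculated per arm as: (# moderate + severe AEs"), divided by the number of clients who attend a follow-up visit on Day 2, 7 or 14. Protocol section 10, Objective 1, has the same numerator over a differently worded denominator: "moderate + severe AEs)/ (total # VMMC clients who attend/responded to 2, 7 or 14 Day follow-up visits or texts". (The difference between the denominators is a separate matter.)

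The text around the formula describes one yes/no result per man:

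- The SAP's power statement concerns "the difference between arms in the proportion with AEs ascertained", and its sample size table comes from a "two-group test of non-inferiority in proportions".
- In SAP item 1, the sentence just before the formula compares the "cumulative proportion (rate) of any moderate or severe AE ascertained" by Day 14, using a one-sided 95% interval for the difference in proportions. If more AEs are seen with texting, Fisher's exact test follows.
- The protocol adds "Multivariate logistic regression models (any AE v none").

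Neither document says in so many words that each man is counted once.

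**The concern.** A count of AEs over a count of men is a number of events per man. It equals a proportion only if no man has more than one event. With repeats, the count does not fit a 2x2 table of men and does not have the binomial variance that an interval for a difference in proportions assumes.

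The formula is the line an analyst would be most likely to program. The AEs are to be taken from routine records and AE forms, so a tally of AE records is an easy slip. Few AEs are expected, so a single repeat could decide whether the primary comparison passes.

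**Working it through.** **1. Reproduce the sample size on a per-man basis.** Inputs from the SAP: control 0.5%, texting 2.0% (or 1.5%), margin 0.25 points, one-sided 5%, power 80%. With the binomial variance p(1-p) per man:

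n = [p1(1-p1) + p2(1-p2)] x [(1.645 + 0.842) / (p2 - p1 + 0.0025)]^2

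- 2.0%: (0.004975 + 0.0196) x (2.487/0.0175)^2 = 496.1, so 497. The SAP has 497.
- 1.5%: (0.004975 + 0.014775) x (2.487/0.0125)^2 = 781.5, so 782. The SAP has 782.

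The sample size therefore already treats the outcome as men with or without an AE.

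**2. How many AEs are in play.** At 497 per arm, 497 x 0.005 = 2.5 control men and 497 x 0.02 = 9.9 texting men are expected to have an AE, about 12.4 in all. A 5% repeat rate would add about 0.6 AEs and a 20% rate about 2.5.

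**3. One repeat at the boundary.** The SAP names no interval method. Assume an unpooled normal interval, 497 per arm, margin -0.25%:

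| Control v texting | Lower limit | Result |
|---|---|---|
| 3 v 6 | -0.384% | fail |
| 3 v 7 | -0.236% | pass |
| 4 v 7 | -0.487% | fail |

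One extra AE in the texting arm turns a fail into a pass, and one extra in the control arm turns it back. For Fisher's test (two-sided, an assumption), 2 v 9 gives p = 0.064 and 2 v 10 gives p = 0.037.

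**4. How often the decision changes.** Assume that each man with an AE has a second one with probability q, the same in both arms. Exact enumeration of binomial counts at 0.5% v 2.0%, normal interval, in percent of trials:

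| q | n = 497: fail to pass + pass to fail | Net | n = 552: fail to pass + pass to fail | Net |
|---|---|---|---|---|
| 0 | 0 | 0 | 0 | 0 |
| 1% | 0.37 + 0.36 | +0.01 | 0.31 + 0.33 | -0.01 |
| 2% | 0.70 + 0.68 | +0.02 | 0.59 + 0.61 | -0.02 |
| 5% | 1.51 + 1.44 | +0.07 | 1.25 + 1.28 | -0.03 |
| 10% | 2.43 + 2.21 | +0.22 | 1.98 + 1.95 | +0.03 |
| 20% | 3.40 + 2.71 | +0.69 | 2.71 + 2.39 | +0.32 |

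At q = 20% the chance of passing goes from 83.8% to 84.5% (497) or from 87.8% to 88.1% (552). With a score interval instead, the decision changes in at most 6.5% of trials (4.08 + 2.45 at 497) and the net change is at most 1.6 points.

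**5. False passes when the true difference equals the margin (0.5% v 0.25%).**

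| Interval, n | Men | Events, q = 5% | Events, q = 20% |
|---|---|---|---|
| Normal, 497 | 9.1% | 9.4% | 10.1% |
| Normal, 552 | 9.4% | 9.9% | 10.8% |
| Score, 497 | 3.7% | 4.2% | 5.3% |
| Score, 552 | 3.5% | 3.9% | 5.0% |

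With the normal interval the rise is at most 1.0 points (497) or 1.3 points (552). The rise depends on the event rates. In a simulation at 2.25% v 2.0%, with 497 per arm and the normal interval, the false-pass rate goes from 5.0% to 6.3% at q = 10% and 7.3% at q = 20%. Those control rates are well above the 0.5% planned.

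**The case against.** The strongest reply is that the intent is plain. The sentence before the SAP formula speaks of a proportion with any moderate or severe AE, the power statement speaks of the proportion with AEs, and the protocol's regression contrasts any AE with none. The numerator may be shorthand for which grades are combined, and a statistician reading the whole paragraph would probably count men. This stands, and it is why the point concerns one formula and not the analysis. It does not make the formula right: as written it gives a different number whenever a man has two AEs.

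It is also fair to say that every non-zero effect above rests on an assumed repeat rate. The protocol's account of Day 14 follow-up says that in an earlier field study "the most common AEs of bleeding and infection were found a mean of 6.7 and 9.0 days" after the procedure. A reader might infer that repeats are to be expected. The text shows only that both kinds fall inside the 14-day window; it does not say that they occurred in the same man.

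Two other stronger readings are tempting and fail. One is that the sample size is wrong; it reproduces with per-man variance. The other is that the numerator produces a false-pass rate of about 10% against a nominal 5%. Most of that excess (9.1-9.4% when men are counted correctly) comes from the assumed normal interval at very low counts. With a score interval the starting value is 3.5-3.7%.

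**Conclusion.** The point holds as a wording error in the formula, in both documents. The rest of the plan settles that men are to be counted, so neither the planned tests nor the sample size is at fault.

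The effect is nil if no man has two moderate or severe AEs by Day 14. Under a 0-20% repeat rate, equal in both arms, and a normal interval at the planned rates, an analyst who applied the formula literally would change the decision in 0-6.1% of trials, with a net change in the chance of passing of at most 0.7 points. The false-pass rate at 0.5% v 0.25% would rise by at most 1.0-1.3 points. The repeat rate and the interval method are assumptions; the documents give neither. Severity: minor.

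**What to change.** In SAP Data Analysis item 1 and protocol section 10, replace the numerator with: *number of men with at least one moderate or severe AE by Day 14 (each man counted once)*. Total AEs per arm may be reported alongside as a description, but that is optional.

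The cost is one phrase in each document. No new data are needed, and sample size, margin and alpha do not change.
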